### **8.3.5 Pregnancy**

All the participants will be confirmed with postmenopausal status including hormonal level at baseline. In case of a suspected pregnancy, a pregnancy test should be performed. In the unlikely event of a pregnancy the following applies:

- Details of all pregnancies in participants will be collected after the start of study intervention and until end of Follow-up.
- If a pregnancy is reported, the investigator will record pregnancy information on the appropriate form and submit it to the sponsor within 24 hours of learning of the pregnancy.

- While pregnancy itself is not considered to be an AE or SAE, any pregnancy complication or elective termination of a pregnancy for medical reasons will be reported as an AE or SAE.
- Abnormal pregnancy outcomes (e.g., spontaneous abortion, fetal death, stillbirth, congenital anomalies, ectopic pregnancy) are considered SAEs, and will be reported as such.
- The participant will be followed to determine the outcome of the pregnancy. The investigator will collect follow-up information on the participant and the neonate and the information will be forwarded to the sponsor.
- Any post-study pregnancy-related SAE considered reasonably related to the study intervention by the investigator will be reported to the sponsor as described in Section 8.3.4. While the investigator is not obligated to actively seek this information in former study participants, he or she may learn of an SAE through spontaneous reporting.
- Any participant who becomes pregnant while participating in the study will discontinue study intervention.

See Section 10.4 for details on collection of pregnancy information.

### 8.3.6 Adverse Events of Special Interest

The following are defined as AESI in this study, if the event takes place after the first intake of study intervention:

- Any condition triggering close liver observation according to Section 10.5.

Any increase in liver enzymes meeting the following criteria needs to be reported as an adverse event to the sponsor within 24 hours of the investigator's awareness for expedited reporting to the health authorities:

- ALT and/or AST  $>8x$  ULN OR
- ALT and/or AST  $>3x$  ULN with total bilirubin  $>2x$  ULN

The investigator may consider whether the observed increase in liver values would qualify as SAE.

- Somnolence or fatigue: Mild somnolence has been identified as a possible adverse reaction to elinzanetant. Participants will be instructed neither to drive nor operate machinery if they experience somnolence or fatigue. As a precautionary measure, participants are dosed in the evening before going to bed.
- Phototoxicity: A signal with respect to potential phototoxicity warrants monitoring of participants for skin reactions to sunlight. In case such a reaction occurs, exposure to strong sunlight should be avoided.
- Post-menopausal uterine bleeding: Any participants experiencing post-menopausal bleeding after randomization should undergo a transvaginal ultrasound with subsequent investigation and management (including endometrial biopsy, if indicated) according to the investigator's clinical judgement and usual practice (unexplained

post-menopausal bleeding prior to randomization will exclude the participant from the study).

## 8.4 Pharmacokinetics

Blood samples for measurement of elinzanetant and its main metabolites in plasma for PK are to be collected at the time points given in [Table 1–3](#). The date and time of study drug intake on the previous dosing days prior to the PK sampling as indicated in [Table 1–3](#), the time of the supervised drug intake, and the time of all blood samples are to be documented.

If, for any reason, PK samples are taken outside of the pre-specified time window, the exact time that the sample was taken has to be recorded. These time deviations are not to be considered as important deviations.

If a participant discontinues study treatment permanently, no blood sampling for PK is required. PK analyses are based on a population modeling approach. Blood samples are considered valid for the population PK analysis under the following conditions:

- The dose amount and time of drug intake prior to the blood sample is known
- The time of the blood sample collection is known.

The samples are to be collected and processed as described in detail in the respective Sample Handling Sheets as a part of a separate Laboratory manual.

Plasma concentrations of elinzanetant are determined using a validated liquid chromatography-tandem mass spectrometry (LC-MS/MS). QC and calibration samples are analyzed concurrently with study samples. The results of calibration samples, QC samples, and study samples will be reported in the Bioanalytical Reports, which will be included in the Clinical Study Report for this study. A re-opening of the database may become necessary in order to include the results of the PK measurements. In addition, selected metabolites may be quantified in plasma using a validated analytical method and evaluated and reported as described for elinzanetant.

The bioanalyst will be unblinded for analysis of study samples. Placebo samples will not be analyzed.

Plasma concentration information that would unblind the study will not be reported to investigative sites or blinded personnel until the study has been unblinded.

### Population pharmacokinetic analysis of elinzanetant

Based on the plasma concentrations, the variability in elinzanetant PK will be analyzed using population PK modeling. Optionally, a population PK/PD model could be used to describe the effect of elinzanetant exposure on PD data related to efficacy and safety such as frequency of VMS and endocrine hormone levels. This analysis might start prior to database lock (eg, at the moment that approximately 80% of the expected PK samples have been measured). The final population PK model that will be applied to describe the PK of elinzanetant in the study population may be linked to relevant PD parameters (eg, frequency of VMS, endocrine hormone levels) obtained in this study to investigate the relationship between elinzanetant exposure and response.

Population or nonlinear mixed effects PK models describe the relationship between dose, time, and the elinzanetant plasma drug concentration. A previously developed population PK model for elinzanetant based on Phase 1 and 2 data will be applied to all valid PK samples to evaluate the relationship between variability in PK and covariates, (ie, intrinsic [eg, body weight, race] and extrinsic factors [eg, concomitant medication]) that are of clinical relevance. If necessary, the population PK model will be adapted to adequately fit the data. Individual PK parameters of elinzanetant will be calculated.

A separate Modeling and Simulation Analysis Plan, providing details of the model development and evaluation will be provided before the start of the population PK analysis. Evaluation of the data will be presented in a separate Modeling and Simulation Report.

Appropriate measures will be taken to maintain blinding of the study team (eg, data access will be restricted to specific people involved in the analysis and members of the study team will neither have access to the randomization list nor to individual data).

## 8.5 Genetics

Genetic as well as non-genetic analyses may be part of the biomarker investigations in this study, if approved by local ECs / IRBs and competent authorities.

Pharmacogenetic investigations may be of any kind, except for whole genome sequencing.

## 8.6 Biomarkers

In this study, genetic as well as non-genetic biomarkers (e.g., related to the mode of action or the safety of the study intervention and similar drugs) may be investigated. This applies to further biomarkers deemed relevant to VMS and associated health problems. These investigations may include e.g., diagnostic, safety, pharmacodynamic, monitoring, or potentially predictive biomarkers.

### PD /safety biomarkers from blood

The following table gives an overview on sample types collected:

Sample type	Description
Biomarker plasma	For PD / safety (optional assessment)
Biomarker serum	For PD / safety (optional assessment)
Biomarker whole blood	For pharmacogenetics testing

- **Timing** – see the SoA planned time points of sample collection. Sampling time points may also be moved or removed.
- **Sample handling and storage** – details on the collection, processing, shipment and storage of samples will be provided in separate documents (e.g. sample handling sheets or lab manual). Samples may be stored for a maximum of 15 years (or according to local regulations) following the end of the study at a facility selected by the sponsor to enable further analyses.
- **Reporting** – the results of biomarker investigations may be reported separately (e.g. in a biomarker evaluation report).

## 8.7 Immunogenicity Assessments

Not applicable

## 8.8 Health Economics

Not applicable

# 9. Statistical Considerations

## 9.1 Statistical Hypotheses

The hypothesis for the primary efficacy endpoint is defined as:

$H_0: \mu_P \leq \mu_V$  versus  $H_1: \mu_P > \mu_V$  where  $\mu_P$  and  $\mu_V$  stand for the mean change in frequency of moderate to severe HF from baseline in the placebo (P) and verum (V) group to Week 12.

The type I error rate will be controlled at a one-sided  $\alpha=0.025$  level.

All other endpoints will be summarized descriptively and therefore no multiplicity adjustment is needed.

## 9.2 Sample Size Determination

Approximately 600 participants will be randomly assigned to study intervention. Of these, 300 participants will be randomly assigned to elinzanetant and the other 300 participants will be randomly assigned to the placebo arm. Assuming an overall drop-out rate of 30% and 10% during the months 1-3 and 4-6 in the elinzanetant arm, approximately 210 participants will be available that were treated for 1 year and approximately 240 participants will be available that were treated for at least 6 months.

The number of participants needed for this study is based on the total number of participants needed for the safety evaluation. Following the ICH E1 guideline ([EMA 1995](#)), a total of 1500 participants are required that were exposed to at least one dose of elinzanetant 120 mg. Of these 1500 participants 300-600 should have been treated for at least 6 months and approximately 100 for 1 year. Based on the number of participants that are available from previous phase 1 and phase 2 studies, together with the number of participants that are planned to be enrolled in upcoming phase 3 studies, the number of participants needed for the elinzanetant arm in this study is 300, also taking into account the assumed drop-out described above.

Screen failures are defined in Section [5.4](#). Assuming a screen failure rate of 30% approximately 860 participants need to be enrolled to achieve the required number of 600 randomized participants. Additionally, further patients may be enrolled in case of an exceptionally high drop-out rate due to a trial-continuity issue.

A formal sample size justification was performed for the primary efficacy endpoint using the one-sided two-Sample T-test (equal variance) assuming at least approximate normal

distribution. Drop-out rate during the first 3 months is assumed to be 10%. The power with treatment differences (ie. mean change in frequency of moderate to severe HF from baseline to Week 12), with N=270 per treatment group and assumed standard deviation are provided in [Table 9–1](#). The data from placebo arm in SWITCH-1 study ([NCT03596762 2020](#)) was used for assumption of standard deviation.

**Table 9–1: Sample size justification**

Standard deviation	Treatment difference Elinzanetant vs. placebo	Power %
4.29	-1.00	77.1 %
	-1.50	98.2 %
	-2.00	>99.9 %

PASS version 13.0.11 was used for sample size calculation.

## 9.3 Analysis Set

For the purposes of analysis, the following analysis sets are defined in [Table 9–2](#).

**Table 9–2: Definition of the analysis sets.**

Analysis Set	Description
Enrolled	All participants who sign the informed consent form.
Full Analysis Set (FAS)	All randomized participants.
Safety Analysis Set (SAF)	All participants who receive at least one dose of study intervention.

Efficacy analyses will be based on the FAS and participants will be analyzed according to the randomized intervention. Safety analyses will be performed on the SAF and participants will be analyzed according to the intervention received.

Documentation of validity findings and assignment of participants to analysis sets will be performed according to the sponsor's applicable Standard Operating Procedures.

Details on additional subsets which may be of interest will be provided in the statistical analysis plan (SAP).

## 9.4 Statistical Analyses

### 9.4.1 General Considerations

SAP will be finalized prior to database lock and will include a more technical and detailed description of the statistical analyses described in this section. This section is a summary of the planned statistical analyses of the most important endpoints including primary and secondary endpoints.

If not otherwise indicated, the statistical analyses will be performed using SAS; the version used will be specified in the SAP.

The endpoints/variables collected in the study will be analyzed using descriptive statistics as appropriate. Continuous variables will be analyzed using at least the following descriptive statistics: number of non-missing observations, arithmetic mean and standard deviation,

median, minimum and maximum. Where appropriate 95 % confidence intervals will be provided. Discrete data will be analyzed using frequency tables. Further details will be described in the SAP.

### **Intercurrent Events**

Important Intercurrent Events (ICEs) for this study are defined as:

- a. Temporary treatment interruption in the week 12 defined as treatment taken <80% during weeks 1-12 OR treatment taken on <5/7 days during either week 11 or 12.
- b. Permanent treatment discontinuation of randomized treatment.
- c. Intake of prohibited concomitant medications having impact on efficacy.

The impact of these ICEs on the study results and its interpretation is addressed in [Table 3–2](#) where the primary estimand for the primary endpoint is defined.

We considered a low impact of the COVID-19 pandemic on missing assessments of the frequency and severity of HF due to the use of eDiary. The eDiary should be completed at home and therefore, there is no need for participants to attend the clinic for the assessment of HF related endpoints.

COVID-19 is included as a reason for occurrence of the important ICEs in the study estimand strategy ([Table 3–2](#)).

### **9.4.2 Primary Endpoint**

The primary efficacy endpoint for this study is mean change in frequency of moderate to severe HF from baseline to Week 12.

#### **9.4.2.1 Calculations related to the frequency and severity of HF**

A diary day for the calculation of the frequency and severity of HF consists of the evening entry and the morning entry of the subsequent day. A day will be considered available for the calculation of the frequency and severity of HF, if at least the evening or the morning entry (of the subsequent day) is not missing. The daily number of hot flashes per day will be calculated as the sum of the evening and morning entries (of the subsequent day). If only the evening or morning entry is available, then only this will be used for that particular day.

The baseline value of frequency and severity of moderate to severe HF will be calculated using the available data assessed via the HFDD during the 14 days prior to the baseline visits. As per inclusion criteria 9, at least 11 days will be available for the derivation of the baseline value.

#### **Baseline value of frequency of moderate to severe HF:**

The baseline value will be calculated by aggregating the available days during the 14 days prior to start of treatment to a mean daily frequency as (total number of moderate to severe HF during the 14 days prior to start of treatment) / (total number of available days with data).

**Frequency of moderate to severe HF during treatment:**

The frequency of moderate to severe HF for each week during the treatment period will be calculated using the available data during that particular week. Specifically, for Week 12, Days 78-84 will be used (Day 1 corresponds to start of treatment). These data will be aggregated to a mean daily frequency as (total number of moderate to severe HF during that week) / (total number of available days with data during that week). In case data is not available for more than 2 days within a week, the value for that particular week will be set to missing. Further details will be specified in the SAP.

**Mean change in frequency of moderate to severe HF from baseline to Week 12/over time:**

This will be calculated as the difference in the frequency of moderate to severe HF at Week 12 or at various weeks, respectively, from the baseline value of the frequency of moderate to severe HF.

**Baseline value of severity of moderate to severe HF:**

The mean daily severity during baseline will be calculated as [(2 x number of moderate HF) + (3 x number of severe HF)] / (total number of moderate to severe hot flashes on that day). When no moderate or severe HF are reported for a particular day, the mean severity for that day will be set to 0. The baseline value will be calculated by averaging the mean daily severity of the available days during the 14 days prior to start of treatment.

**Severity of HF during treatment:**

The mean daily severity during treatment will be calculated as [(1 x number of mild HF) + (2 x number of moderate HF) + (3 x number of severe HF)] / (total number of mild, moderate and severe hot flashes on that day). When no HF are reported for a particular day, the mean severity for that day will be set to 0.

Similar to the frequency, the severity of HF for each week during the treatment period will be calculated using the available data during that particular week. To obtain the post-baseline severity of HF during a particular week, the weekly data will be aggregated by averaging the mean daily severity of HF of the available days during that week. In case data is not available for more than 2 days within a week, the value for that particular week will be set to missing. Further details will be specified in the SAP.

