**Mean change in severity of moderate to severe HF from baseline over time:**

This will be calculated as the difference in the severity of HF at various weeks, respectively, from the baseline value of the severity of moderate to severe HF.

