#### Baseline value of severity of moderate to severe HF:

The mean daily severity during baseline will be calculated for available days as [(2 x number of moderate HF) + (3 x number of severe HF)] / (total number of moderate to severe hot

flashes on that day). When no moderate or severe HF are reported for a particular day, the mean severity for that day will be set to 0. The baseline value will be calculated by averaging the mean daily severity of the available days during the 14 days prior to start of treatment. As per inclusion criteria 9 (see protocol), at least 11 days will be available for the derivation of the baseline value.

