#### **Severity of HF during treatment:**

The mean daily severity during treatment will be calculated for available days as  $[(1 \times \text{number of mild HF}) + (2 \times \text{number of moderate HF}) + (3 \times \text{number of severe HF})] / (\text{total number of mild, moderate and severe hot flashes on that day})$ . When no HF are reported for a particular day, the mean severity for that day will be set to 0.

Similar to the frequency, the severity of HF for each week during the treatment period will be calculated using the available data during that particular week. To obtain the post-baseline severity of HF during a particular week, the weekly data will be aggregated by averaging the mean daily severity of HF of the available days during that week. In case data is missing for more than 2 days within a week, the value for that particular week will be set to missing.

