#### **Mean change in severity of moderate to severe HF from baseline over time:**

This will be calculated as the difference in the mean daily severity of HF at various weeks, from the baseline value of the severity of moderate to severe HF.

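### Hot flash severity leaves out mild episodes at baseline but counts them on treatment, so a woman whose hot flashes do not change can show a severity change in either direction

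*Protocol*

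**What the plan says.** Protocol 9.4.2.1 defines three quantities for severity.

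- **Baseline.** "The mean daily severity during baseline will be calculated as [(2 x number of moderate HF" with severe episodes weighted 3, divided by the moderate and severe total for the day. Mild episodes are in neither numerator nor denominator. The zero rule is: "When no moderate or severe HF are reported for a particular day, the mean severity for that day will be set to 0". A mild-only day therefore scores 0.
- **On treatment.** "The mean daily severity during treatment will be calculated as [(1 x number of mild HF" with moderate weighted 2 and severe weighted 3, divided by the total of all three grades. The zero rule is: "When no HF are reported for a particular day, the mean severity for that day will be set to 0". A mild-only day therefore scores 1.
- **Change.** The "difference in the severity of HF at various weeks, respectively, from the baseline value of the severity of moderate to severe HF".

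SAP 5.1.2.1 repeats the rule. At baseline: "The mean daily severity during baseline will be calculated for available days as [(2 x number of moderate HF". On treatment: "The mean daily severity during treatment will be calculated for available days as", followed by the all-grade formula. The change is the "difference in the mean daily severity of HF at various weeks, from the baseline value of the severity of moderate to severe HF".

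The endpoint keeps a name that refers to moderate-to-severe hot flashes (Protocol Table 3-1, SAP Table 1-1). SAP 5.5.1 plans by-arm change, percentage change and plots of the proportion of women reaching each size of change. It is exploratory and descriptive (Protocol 9.1, SAP 5.5). No same-formula severity analysis is planned, and neither document explains the two formulas.

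**The concern.** A change score should be zero when nothing has changed. Here the two ends are measured on different scales, so part of each woman's change reflects the scoring rule and not her symptoms. Both directions are possible. Mild episodes on a day with moderate or severe ones pull the on-treatment mean down, which looks like improvement. Mild-only days move from 0 to 1, which looks like worsening. Such days can occur at baseline because inclusion criteria 3 and 9 set no minimum daily count, although nothing in the documents shows that they are common.

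At stake is the reading of the severity tables and plots in SAP 5.5.1 wherever they are read within an arm, as a percentage, or at a chosen size of change.

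**Working it through.** **Inputs.** The formulas and zero rules are those of Protocol 9.4.2.1 and SAP 5.1.2.1. The documents state no figure for this point and no mild counts, so every pattern below is an assumption.

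**Formulas.** For a day with m mild, o moderate and s severe episodes:

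- baseline score M = (2o + 3s)/(o + s), or 0 if o + s = 0;
- on-treatment score A = (m + 2o + 3s)/(m + o + s), or 0 if there are none.

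For an unchanged day with o + s > 0, A - M = -[m/(m + o + s)] x (M - 1). For an unchanged mild-only day, A - M = +1.

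**Single unchanged day**

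| (m, o, s) | M | A | Change |
|---|---|---|---|
| (0,5,2) | 16/7 = 2.286 | 2.286 | 0 |
| (1,5,2) | 2.286 | 17/8 = 2.125 | -0.161 (-7.0%) |
| (3,5,2) | 2.286 | 19/10 = 1.900 | -0.386 (-16.9%) |
| mild only | 0 | 1 | +1.0 |

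For mild shares of 10% to 50% and M between 2 and 3, the shift on a mixed day runs from -0.10 to -1.00.

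**Unchanged woman: 14 baseline days, treatment week with the same mix**

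| Baseline days | Baseline | On treatment | Change |
|---|---|---|---|
| 12 x (3,5,2) + 2 mild-only | 1.959 | 1.771 | -0.188 (-9.6%) |
| 12 x (1,5,2) + 2 mild-only | 1.959 | 1.964 | +0.005 |
| 10 x (1,5,2) + 4 mild-only | 1.633 | 1.804 | +0.171 (+10.5%) |

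If the mixed days shift by -d, the sign turns when the share q of mild-only days satisfies q = (1 - q)d, so q = d/(1 + d). That gives 0.161/1.161 = 14% and 0.386/1.386 = 28%.

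**Like-for-like check.** With one formula at both times, the change is exactly 0 in every unchanged case.

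**Between arms.** Write A_t for all-grade severity on treatment, and A_0 and M_0 for the all-grade and moderate-to-severe baselines. Then A_t - M_0 = (A_t - A_0) + (A_0 - M_0). The last term depends only on baseline data. Under randomization it cancels in expectation from the difference in mean change, even if treatment alters the mild share.

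Percentage change has no such protection, because the denominator is M_0. A difference of -0.30 is -0.30/1.900 = -15.8% on the all-grade baseline, but -0.30/2.286 = -13.1% on the moderate-to-severe one.

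**Proportion plots.** Assume normal changes with means -0.3 (placebo) and -0.6 (elinzanetant), SD 0.4, and an added offset. The gap is the between-arm difference in the proportion reaching the stated reduction, in percentage points.

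| Offset | Gap at 0.5 | Gap at 1.0 |
|---|---|---|
| 0 | 29.0 | 11.9 |
| -0.161 | 28.2 | 18.6 |
| -0.386 | 20.9 | 27.0 |
| +0.171 | 25.3 | 6.2 |
| half -0.386, half 0 | 24.9 | 19.4 |

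The difference in means is -0.30 in every row.

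**The case against.** The strongest case is that the rule is deliberate and its consequences are small. Protocol and SAP agree, the rule stands in the fourth SAP version, and an earlier protocol version answered FDA feedback from a Special Protocol Assessment. The documents do not say whether that feedback covered severity. A sensible motive can be supplied: baseline grades the qualifying symptom, and counting mild episodes on treatment stops a mild-only week from scoring the same as a symptom-free one. The endpoint is untested, and Protocol 4.2 makes the placebo comparison the measure of effect. The plots have no responder threshold, and a common offset only slides both absolute-change curves sideways by the same amount. All-grade frequency is already reported with one formula throughout (SAP 5.5.1). An all-grade severity score also has a flaw of its own: a woman who loses only mild episodes scores as worse.

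Much of this stands and limits the weight of the point. The rule is not a transcription slip, nothing confirmatory is touched, and the fixed-cut-off gaps above are illustrations, not estimates. Agreement between the documents does not put both ends of the change on one scale, however. All-grade frequency shows whether mild episodes changed but does not correct the severity outputs. The flaw in the all-grade score is a reason to show both versions.

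**Conclusion.** The concern holds. The mechanism follows from the formulas alone and can act in either direction; a woman with no mild episodes shows no artefact. In the assumed patterns for an unchanged woman it runs from -0.19 to +0.17 over a mix of days, and for single days it reaches -0.39 or +1.0. Actual size and sign depend on the mild counts, which the documents do not give.

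The artefact affects within-arm change, percentage change and the proportion-achieving plots. It does not bias the between-arm difference in mean change, provided the women contributing data remain comparable between arms at baseline. No imputation is planned for this endpoint, so differential dropout could leave some residue; its size was not assessed. The primary frequency endpoint, alpha and power are unaffected. This is a worthwhile correction to a descriptive endpoint and does not threaten the trial's main conclusion.

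**What to change.** Keep the protocol-defined severity change and report a same-formula version beside it. Its baseline would be (1 x mild + 2 x moderate + 3 x severe) divided by all hot flashes that day, set to 0 only when none of any grade is reported. Provide the matching change, percentage change and plots. Label each version so that its name matches its formula, and if the different baseline formula is intended, say why.

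No new data are needed. The diary records mild counts from SCR-2 (SAP 6.2.1), and they already feed the baseline all-grade frequency (SAP 5.5.1). The cost is one derivation and some extra output.

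The within-arm change may look smaller or larger than in the protocol version. The all-grade version should not replace it: going from (3,5,2) to (0,5,2) raises the all-grade score from 1.900 to 2.286 (+0.386), although the woman has only lost mild episodes, while the protocol version scores her 0.
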